2.4.5.1 Analyses of adverse events

Generalities

The primary focus of adverse event reporting will be on TEAEs. Pre-treatment and post-treatment adverse events will be described separately.

If an adverse event date/time of onset (occurrence, worsening, or becoming serious) is incomplete, an imputation algorithm will be used to classify the adverse event as pre-treatment, treatment-emergent, or post-treatment. The algorithm for imputing date/time of onset will be conservative and will classify an adverse event as treatment emergent unless there is definitive information to determine it is pre-treatment or post-treatment. Details on classification of adverse events with missing or partial onset dates are provided in [Section 2.5.3](#).

Adverse event incidence tables will present the number (n) and percentage (%) of patients experiencing an event by treatment group. Multiple occurrences of the same event in the same patient will be counted only once in the tables within a treatment phase. The denominator for computation of percentages is the safety population within each treatment group. Sorting will be based on results for the SAR440340 and dupilumab coadministration group by the following orders:

- Tables presented by SOC: sorted by internationally agreed SOC order
- Tables presented by PT: sorted by decreasing frequency of PT
- Tables presented by SOC and PT: sorted by internationally agreed SOC order and decreasing frequency of PT within SOC
- Tables presented by SOC, HLGT, HLT, and PT: sorted by internationally agreed SOC order and then alphabetical order of HLGT, HLT, and PT

Analysis of all TEAEs

The following TEAE summaries will be generated for the safety population.

- Overview of TEAE, summarizing number (%) of patients with any
 - TEAE
 - Severe TEAE
 - Serious TEAE
 - TEAE leading to death
 - TEAE leading to permanent treatment discontinuation
- All TEAEs by primary SOC
- All TEAEs by primary SOC, HLGT, HLT, and PT
- All TEAEs by primary SOC and PT
- All TEAEs by PT
- All TEAEs related to SAR440340 or matching placebo by primary SOC, HLGT, HLT and PT
- All TEAEs related to dupilumab or matching placebo by primary SOC, HLGT, HLT and PT
- All TEAEs by maximal severity, presented by primary SOC and PT
- Listing of all TEAEs

Analysis of all treatment emergent SAEs

- All treatment-emergent SAEs by primary SOC, HLGT, HLT, and PT
- All treatment-emergent SAEs by primary SOC and PT
- All treatment-emergent SAEs by PT

- All treatment-emergent SAEs related to SAR440340 or matching placebo by primary SOC, HLGT, HLT and PT
- All treatment-emergent SAEs related to dupilumab or matching placebo by primary SOC, HLGT, HLT and PT
- Listing of all treatment-emergent SAEs

Analysis of all TEAEs leading to permanent treatment discontinuation

- All TEAEs leading to permanent treatment discontinuation by primary SOC, HLGT, HLT, and PT
- All TEAEs leading to permanent treatment discontinuation by primary SOC and PT
- All TEAEs leading to permanent treatment discontinuation by PT
- Listing of all TEAEs leading to permanent treatment discontinuation

Analysis of AESI

A summary of number of patients with any TEAE by AESI category (defined by the search criteria in [Section 2.1.4.1](#)) will be generated. In addition, for each AESI category the following will be provided:

- All TEAEs by PT
- Overview summary including
 - Number (%) of patients with any TEAE
 - Number (%) of patients with any SAE (regardless of treatment emergent status)
 - Number (%) of patients with any treatment-emergent SAE
 - Number (%) of patients with any AE leading to death
 - Number (%) of patients with any TEAE leading to permanent study drug discontinuation
 - Number (%) of patients with any TEAE related to IMP reported by investigator
 - Number (%) of patients with any TEAE by maximum intensity, corrective treatment, and final outcome
 - Number of TEAE adjusted by the exposure duration

For categories with at least 5 events in at least one treatment group, K-M plots of time to first event will be provided to depict the course of onset over time.

Analysis of pre-treatment and post-treatment adverse events

Listings will be provided for all pre- and post-treatment AEs. The following summaries may be generated if the number of events is large enough:

- All pre-treatment AEs by primary SOC and PT

- All pre-treatment SAEs by primary SOC and PT
- All pre-treatment AEs leading to treatment discontinuation by primary SOC and PT
- All pre-treatment AEs leading to death by primary SOC and PT
- All post-treatment AEs by primary SOC and PT
- All post-treatment SAEs by primary SOC and PT
- All post-treatment AEs leading to death by primary SOC and PT

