	
estimated to be 0.14 L. The observed effect of dupilumab versus placebo was 0.27 L.
 
Randomization will be stratified by Screening Visit 1 eosinophil count and by country.
 
To ensure enrollment according to intended distribution of baseline eosinophil count, alerts will be built into the interactive voice/web response system (IVRS/IWRS) to limit enrolling patients in the following 2 stratification groups:
 
Eosinophil <150/mm^3: not more than approximately 25% (60) patients
 
Eosinophil ≥300/mm^3: at least approximately 45% (108) patients
 
Analysis population:
 
The primary population for efficacy analysis will be all randomized patients receiving at least one dose of study drug, analyzed in their assigned group (modified intent-to-treat [mITT]).
 
The safety population is defined as all patients who have received at least one dose of the IMP, analyzed according to the treatment actually received.
 
Primary analysis:
 
For the primary analysis of proportion of patients experiencing an LOAC event, a logistic regression model will be used to compare SAR440340 with placebo and the coadministration of SAR440340 and dupilumab with placebo. The model will include terms for treatment stratification factors, baseline background ICS dose level and number of exacerbation events within 1 year prior to screening. The odds ratio and 95% confidence interval will be estimated from this model.
 
Safety analysis:
 
Safety analyses will be descriptive, based on the safety population. The safety analysis will focus on the TEAE period. This period is defined as the time from the first administration of the IMP to the last administration of the IMP plus 22 weeks.
 
Interim analyses:
 
No formal interim analysis is planned. Analyses will be performed for safety monitoring and internal decision making. No formal stopping rules or adjustment for multiplicity will be applied.

DURATION OF STUDY PERIOD (per patient)	
The total duration of the study (per patient) is expected to be up to 36 weeks:
 

• 4 weeks (±3 days) of screening period

• 12 weeks (±3 days) of randomized IMP treatment period

 
20 weeks (±5 days) of post IMP treatment safety follow-up period

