2.1.4 Safety endpoints

The safety analysis will be based on the reported adverse events (AEs) and other safety information, such as clinical laboratory data, vital signs, electrocardiogram (ECG), etc.

Observation period

The observation period will be divided into 4 epochs:

- The **screening** epoch is defined as the time from the signed informed consent date up to the first administration of the IMP.
- The **treatment** epoch is defined as the time from the first administration of the IMP to the last administration of the IMP + 14 days.
- The **residual treatment** epoch is defined as the time from the last administration of the IMP + 15 days to the last administration of the IMP + 154 days.

The treatment-emergent adverse event (TEAE) period will include both **treatment** and **residual treatment** epochs.

- The **post-treatment** epoch is defined as the period of time starting the day after the end of the treatment-emergent adverse event period up to the patient's end of study (defined as last protocol-planned visit or the resolution/stabilization of all serious adverse events and adverse events with pre-specified monitoring).

The on-study observation period is defined as the time from start of treatment until the end of the study.

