2.1.4.1 Adverse events variables

Adverse event observation period

- Pre-treatment adverse events are adverse events that developed or worsened or became serious during the screening epoch.
- Treatment-emergent adverse events are adverse events that developed or worsened or became serious during the treatment-emergent adverse event epoch.
- Post-treatment adverse events are adverse events that developed or worsened or became serious during the post-treatment epoch.

All adverse events (including serious adverse events and adverse events with pre-specified monitoring) will be coded to a lower-level term (LLT), preferred term (PT), high-level term (HLT), high-level group term (HLGT), and associated primary system organ class (SOC) using the version of MedDRA currently in effect at Sanofi at the time of database lock.

Adverse event of special interest (AESI) and other selected AE groupings will be searched based on criteria in [Table 3](#):

Table 3 Criteria for adverse events of special interest and other selected AE groupings

AE Grouping	Criteria
AESI	
Anaphylactic reaction (medically reviewed)	Anaphylactic reaction algorithmic approach (Introductory Guide for Standardised MedDRA Queries (SMQs) Version 20.0): includes anaphylactic reaction narrow SMQ (20000021) terms and programmatic identification of cases based on occurrence of at least two preferred terms meeting the algorithm criteria occurring within 24 hours of each other. The latter cases identified using the algorithm will undergo blinded medical review taking into account the timing of events relative to each other and to IMP administration for final determination of an anaphylactic reaction or not.
Hypersensitivity (medically reviewed)	SMQ hypersensitivity (20000214) narrow search and [AE corrective treatment/therapy='Y' or Action taken with IMP='Drug withdrawn' or Action taken with IMP='Drug interrupted'] followed by blinded medical review (documented process) for selection of relevant systemic events
Injection site reaction (serious or severe and lasting 24 hours or longer)	HLT = 'Injection site reaction' and either with serious status, or non-serious events with (AE end date/time - AE start date/time) \geq 24 hours or ongoing and at least one of the following checked on the Injection Site Reaction Complementary Form: 
 - Diameter of at least 10cm - Prevents daily activities - Presence of ulceration or necrosis - Operative intervention required

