2.4.3 Extent of investigational medicinal product exposure and compliance

The overall extent of IMP exposure and compliance will be assessed and summarized by actual treatment within the safety population ([Section 2.3.2](#)).

2.4.3.1 *Extent of investigational medicinal product exposure*

The extent of IMP exposure will be assessed by the duration of IMP exposure.

Duration of IMP exposure is defined as last dose date – first dose date + 14 days, regardless of unplanned intermittent discontinuations (see [Section 2.5.3](#) for calculation in case of missing or incomplete data).

Duration of IMP exposure will be summarized descriptively as a quantitative variable (number, mean, SD, median, Q1, Q3, minimum, and maximum). In addition, duration of treatment exposure will also be summarized categorically by numbers and percentages of patients in each of the following categories and cumulatively according to these categories:

- >0 and \leq 2 weeks
- >2 and \leq 4 weeks
- >4 and \leq 8 weeks
- >8 weeks and < 12 weeks – 3 days
- \geq 12 weeks – 3 days

Additionally, the cumulative duration of treatment exposure will be provided, defined as the sum of the duration of treatment exposure for all patients, and will be expressed in patient years.

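### The exposure-adjusted AESI count takes events up to last dose + 154 days but divides by exposure that ends at last dose + 14 days

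*SAP*

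**What the plan says.** The AESI overview in SAP 2.4.5.1 lists, for each category, a "Number of TEAE adjusted by the exposure duration". No formula, unit or denominator is given there.

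**Numerator.** SAP 2.1.4.1 says: "Treatment-emergent adverse events are adverse events that developed or worsened or became serious during the treatment-emergent adverse event epoch". Under SAP 2.1.4 that period joins the treatment epoch, which ends at last dose + 14 days, to the residual treatment epoch, which runs "from the last administration of the IMP + 15 days to the last administration of the IMP + 154 days". The protocol's Clinical Trial Summary agrees: "This period is defined as the time from the first administration of the IMP to the last administration of the IMP plus 22 weeks".

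**Denominator.** SAP 2.4.3.1 gives the only definition of exposure: "Duration of IMP exposure is defined as last dose date – first dose date + 14 days, regardless of unplanned intermittent discontinuations". The same section sums it over patients into patient-years. SAP 2.5.3 uses the term exposure duration for this same treatment duration. Neither document defines person-time for the treatment-emergent period.

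**The concern.** A rate is interpretable only if the events and the time come from the same window. A programmer who follows the SAP would divide events from the longer window by time from the shorter one.

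Two things are at stake. First, the absolute rate would be too high, and would mislead anyone who sets it beside a correctly computed rate from another study. Second, the error need not be equal across arms. A patient with LOAC is withdrawn from study treatment (SAP 1.1; Protocol 10.3.3), which shortens exposure but leaves the 140-day tail in place. If LOAC is commonest on placebo, as the sample size assumes, the placebo rate is inflated most and an active arm looks relatively safer than it is. Infection is one of the AESI categories, and Protocol 4.5 names a theoretical infection risk for coadministration.

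**Working it through.** **Inputs**

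- Doses at Visits 2, 4, 6, 8, 10 and 12, that is Days 1, 15, 29, 43, 57 and 71 (visit text, Protocol 10.1.2).
- Exposure = last dose − first dose + 14 days (SAP 2.4.3.1).
- Treatment-emergent period = last dose − first dose + 154 days (SAP 2.1.4).
- LOAC 40% on placebo and 14% on SAR440340 (SAP 1.3; Protocol 11.1).
- ICS step-down starts at Week 6, Day 43 (Table 1 in both documents).

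**Check against the plan's own figures.** 22 weeks × 7 = 154 days. For a completer, exposure = 70 + 14 = 84 days and the event window = 70 + 154 = 224 days. Protocol 6.2.1 gives 84 + 140 = 224 days, and Protocol 6.2.2 puts end of study at Day 225 = 71 + 154. All agree.

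**Per patient.** Factor = event window / exposure, where the window is exposure + 140.

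| Doses received | Exposure (d) | Event window (d) | Factor |
|---|---|---|---|
| 6 | 84 | 224 | 2.67 |
| 5 | 70 | 210 | 3.0 |
| 4 | 56 | 196 | 3.5 |
| 3 | 42 | 182 | 4.33 |
| 2 | 28 | 168 | 6.0 |
| 1 | 14 | 154 | 11.0 |

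**Per arm.** Assume an equal constant event rate in both arms, full follow-up, and that all patients without LOAC complete. With LOAC proportion p and exposure e at the stop, mean exposure E = (1 − p) × 84 + p × e, and the arm factor = (E + 140)/E.

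Example, e = 56:

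- Placebo: E = 0.60 × 84 + 0.40 × 56 = 72.8; factor 212.8/72.8 = 2.92.
- SAR440340: E = 0.86 × 84 + 0.14 × 56 = 80.08; factor 220.08/80.08 = 2.75.
- Apparent ratio SAR440340/placebo = 0.94, where the truth is 1.00.

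| Exposure at LOAC stop (d, assumed) | Placebo factor | SAR440340 factor | Apparent ratio | Ratio of unadjusted events per patient |
|---|---|---|---|---|
| 84 | 2.67 | 2.67 | 1.00 | 1.00 |
| 70 | 2.79 | 2.71 | 0.97 | 222.04/218.4 = 1.02 |
| 56 | 2.92 | 2.75 | 0.94 | 220.08/212.8 = 1.03 |
| 42 | 3.08 | 2.79 | 0.91 | 218.12/207.2 = 1.05 |

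The 56-, 70- and 84-day rows have a last dose on Day 43, 57 or 71, so the stop falls after ICS withdrawal begins. The 42-day row has a last dose on Day 29 and a stop before Day 43. Whenever stops shorten exposure, the adjusted ratio lies further from 1.00 than the unadjusted one and on the other side of it.

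**If events are not spread evenly.** Let r be the share of events with onset in the residual epoch. Inflation over the on-treatment rate is 1/(1 − r): 1.0 if r = 0, 2.0 if r = 0.5, and 2.67 if r = 140/224 = 0.625.

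**If follow-up is incomplete.** With 15% of completers lacking the 140-day follow-up, the factor is 1 + 140 × 0.85/84 = 2.42. A LOAC stop immediately after the sixth dose, with 140 days of follow-up, gives 210/84 = 2.5.

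**The case against.** The strongest reply is that little turns on this line. SAP 2.4.5 calls the safety analysis essentially descriptive, with no systematic testing planned. The arms have about 60 patients each. With 10 events per arm (an assumption), a 95% Poisson interval around a rate ratio of 1 runs from 0.42 to 2.40, so a shift of up to 6% would not be visible. That stands for the comparison between arms. It does not answer the error in the absolute rate.

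It can also be said that SAP 2.4.5.1 does not define its denominator, so the authors may have meant time at risk. That is possible, but the SAP defines one exposure duration only and uses the same term for it elsewhere. The text needs changing on either reading.

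Four stronger readings are tempting, and the documents do not support them:

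- *That this is the only safety summary that handles unequal follow-up.* The same section plans Kaplan-Meier plots of time to first event for categories with at least 5 events in a group, and these do not use the disputed denominator. This is only the sole exposure-adjusted event count.
- *That 2.7-fold is a floor.* Follow-up starts from an individual end-of-treatment visit held as soon as possible after a stop (Protocol 6.1.2) and takes place if possible (Protocol 8.2.1), so the factor can be lower. Protocol 10.6.1 places allergic reactions within hours of dosing. For hypersensitivity and injection site reactions the factor may be near 1.
- *That the distortion between arms is large.* A ratio of 0.91 or lower needs all LOAC stops to come before ICS withdrawal, whereas the design provokes LOAC by withdrawing LABA from Week 4 and ICS from Week 6. If LOAC patients' end-of-treatment visit comes 7 days after the last dose, with 140 days of follow-up from there, the ratios for 56, 70 and 84 days become 0.95, 0.98 and 1.01. In the 56-day case the order of the arms reverses if somewhat over 30% of LOAC stops have no follow-up.
- *That the same figures hold for coadministration.* The documents give no planned LOAC rate for that arm.

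**Conclusion.** The mismatch is real and follows from the SAP's own definitions: 140 days of countable events per fully followed patient have no matching denominator time.

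The main effect is on the absolute rate. It is 2.67-fold for a completer, assuming a constant event rate and full follow-up. That suits categories such as infection or malignancy better than dosing-linked ones.

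The effect between arms is modest: an apparent SAR440340/placebo ratio of about 0.94 to 1.00 under equal true rates. This assumes 40% against 14% LOAC, stops at 56 to 84 exposure days, and completion by everyone else. The usual direction favours the active arm, but differential loss to follow-up could change it.

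Patient counts and percentages and the primary efficacy analysis do not use this denominator. The line should be corrected because, as written, it defines a rate that cannot be read per unit of time at risk.

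**What to change.** In SAP 2.4.5.1, state the denominator and its unit, and match the windows in one of two ways:

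1. Divide treatment-emergent events by time at risk in the treatment-emergent period, from first dose to the earlier of last dose + 154 days and last contact.
2. Keep exposure as defined in SAP 2.4.3.1 and count only events in the treatment epoch, to last dose + 14 days.

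The second suits dosing-linked categories such as hypersensitivity and injection site reactions. For those, the first would dilute the rate by adding time in which few events are expected. The SAP could assign one option to each category.

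The cost is one sentence and one derived variable, with no new data. The change is best made before the core database lock described in SAP section 4.

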2.4.5.2 Deaths

The following summaries of deaths will be generated for the safety population depending on the overall incidence.

- Number (%) of patients who died by study period (on-study, on-treatment, post-study)
- TEAEs leading to death (death as an outcome on the adverse event case report form page as reported by the Investigator) by primary SOC, HLGT, HLT, and PT
- Listing of all AEs leading to death

In addition, summary of deaths in non-randomized patients or randomized but not treated patients may be generated.

2.4.5.3 Analyses of laboratory variables

The summary statistics (including number, mean, median, Q1, Q3, SD, minimum and maximum) of all laboratory variables (central laboratory values and changes from baseline) will be calculated for each visit or study assessment (baseline, each post-baseline time point, and last on-treatment) by treatment group. For each continuous parameter listed in [Section 2.1.4.3](#), mean changes from baseline with the corresponding standard error will be plotted over time in each treatment group. This section will be organized by biological function as specified in [Section 2.1.4.3](#).

The incidence of PCSAs (list provided in [Appendix A](#)) at any time during the TEAE period will be summarized by biological function and treatment group whatever the baseline level and/or according to the following baseline status categories:

- Normal/missing
- Abnormal according to PCSA criterion or criteria

For parameters for which no PCSA criteria are defined, similar table(s) using the normal range will be provided.

Laboratory measurements obtained at either scheduled or unscheduled visits will be used in analyses of PCSA. In addition, both centralized and local test results will be used. Centralized data will be used preferentially to the local measures in the analysis when several measurements are performed on the same date and at the same time for a given laboratory test.

Listings will be provided with flags indicating the out of range values as well as the PCSA values.

Potential drug-induced liver injury

If there is any imbalance in the incidence of liver-related adverse events across the treatment groups, the following analysis of liver-related adverse events will be performed.

The liver function tests, namely AST, ALT, alkaline phosphatase, and total bilirubin will be used to assess possible drug-induced liver toxicity. The proportion of patients with PCSA values at any post-baseline visit will also be displayed by duration of exposure for each treatment group.

Time to onset of the initial ALT and AST elevation ($>3 \times \text{ULN}$) and total bilirubin elevation ($>2 \times \text{ULN}$) will be analyzed using Kaplan-Meier estimates presented by treatment group. A graph of distribution of peak values of ALT versus peak values of total bilirubin will also be presented on a logarithmic scale. The graph will be divided into 4 quadrants with a vertical line corresponding to $3 \times \text{ULN}$ for ALT and a horizontal line corresponding to $2 \times \text{ULN}$ for total bilirubin.

Listings of selected laboratory parameters for possible Hy's law cases identified by treatment group (eg, patients with any elevated ALT $>3 \times \text{ULN}$, and associated with an increase in bilirubin $\geq 2 \times \text{ULN}$) will be provided.

The normalization (to $\leq 1 \times \text{ULN}$) or return to baseline (if baseline is $>\text{ULN}$) of elevated liver function tests will be summarized by categories of elevation ($>3 \times \text{ULN}$, $>5 \times \text{ULN}$, $>10 \times \text{ULN}$, $>20 \times \text{ULN}$ for ALT and AST, $>1.5 \times \text{ULN}$ for alkaline phosphatase, and $>1.5 \times \text{ULN}$ and $>2 \times \text{ULN}$ for total bilirubin) with the following categories of normalization: never normalized, normalized despite treatment continuation of IMP, or normalized after IMP discontinuation. A patient will be counted only under the maximum elevation category.

Change in blood eosinophil

Mean changes from baseline in eosinophil count will be summarized and plotted (with corresponding standard error) over time in each treatment group for patients with baseline blood eosinophil $< 0.5 \text{ Giga/L}$ and patients with baseline blood eosinophil $\geq 0.5 \text{ Giga/L}$. Number (%) of patients with post-baseline peak blood eosinophil $\geq 1 \text{ Giga/L}$ and $< 3 \text{ Giga/L}$, $\geq 3 \text{ Giga/L}$ and $< 5 \text{ Giga/L}$, and $\geq 5 \text{ Giga/L}$ will also be summarized in each treatment group and by baseline blood eosinophil status (All, $< 0.5 \text{ Giga/L}$, $\geq 0.5 \text{ Giga/L}$).

